1.3.2 Cohort B

Table 2 Study Schedule of Activities – Cohort B

Study Period:	Screening	Intervention				EOT	Posttreatment			Notes
Visit Number/Title:	Screening	Cycle 1		Cycle 2 onwards*			Safety FU	Efficacy FU	Survival FU	*Cycles 2 to 17 for Q6W schedule; Cycle 2 to 35 for Q3W schedule.
Cycle Day	Up to 28 days prior to first dose	1	Day 22 (Q6W regimens only)	1	Day 22 (Q6W regimens only)	DC	30 days after last dose			
Scheduling Window (days):	-28 to -1	+3	±3	±3	±3		+7	Q9W ±7	Q12W ±14	
Administrative Procedures										
Informed Consent	X									If the investigator plans to treat beyond disease progression, the participant or their legally acceptable representative will be asked to provide documented informed consent (see Section 8.1.1.1).
Informed Consent for Future Biomedical Research (optional)	X									To be obtained after consenting to the main study.
Inclusion/Exclusion Criteria	X	X								
Participant Identification Card	X	X								Add the allocation number at the time of allocation.
Demographics and Medical History	X									
Oncologic Medical History (oncology disease status, MSI/MMR status and prior oncology treatment history including surgery)	X									
RAS (KRAS and NRAS) and BRAF mutation status	X									Results must be obtained by the site before C1D1 allocation. Only perform if status is not already known. Perform per institutional standards.

Study Period:	Screening	Intervention				EOT	Posttreatment			Notes
Visit Number/Title:	Screening	Cycle 1		Cycle 2 onwards*			Safety FU	Efficacy FU	Survival FU	*Cycles 2 to 17 for Q6W schedule; Cycle 2 to 35 for Q3W schedule.
Cycle Day	Up to 28 days prior to first dose	1	Day 22 (Q6W regimens only)	1	Day 22 (Q6W regimens only)	DC	30 days after last dose			
Scheduling Window (days):	-28 to -1	+3	±3	±3	±3		+7	Q9W ±7	Q12W ±14	
Prior/Concomitant Medication Review	X	X	X	X	X	X	X			Record concomitant medications beyond 30 days after treatment discontinuation if related to an SAE or ECI.
Randomization (via IRT)		X								To be completed after confirmation of eligibility.
Study Medication Administration		X		X*						*Required every 6 weeks for participants randomized to the MK-1308A or pembrolizumab monotherapy arms and every 3 weeks for participants randomized to the MK-4280A, MK-7684A, or MK-4830+pembrolizumab arms. Refer to Section 6.1.1.1 for study intervention information for participants in closed arms.

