Vital Signs (temperature, HR, RR, DBP, SBP)	X	X	X	X	X	X	X			BP and pulse rate will be measured after the participant has been resting for 5 minutes. Include pulse oximetry (SpO2) if locally required.
12-lead ECG	X		X*	X*	X*	X				*As clinically indicated.
ECOG Performance Status	X	X	X	X	X	X	X			Must be performed within 3 days of C1D1 treatment and before treatment at each cycle.
AE/SAE review	X									AEs monitored up to 30 days after last dose. SAEs monitored up to 90 days and pregnancy monitored up to 120 days after last dose, or 30 days after last dose if participant starts a new anticancer therapy, whichever is sooner. Refer to Section 8.3 for safety monitoring information for participants in closed arms.
Laboratory Assessments										
Hematology/Chemistry	X	X*	X	X	X	X	X			Collect Predose. *Collect within 72 hours before first study intervention dose.
Urinalysis	X	X*	X*	X*	X*	X*	X			*As clinically indicated Collect within 72 hours before first study intervention dose.
Serum or Urine Pregnancy test (WOCBP only)	X	X		X		X	X			WOCBP require a negative test prior to allocation. If more than 24 hours for a urine test or 72 hours for a serum test have elapsed prior to the first dose of study intervention, another pregnancy test is required. See country-specific requirements in Appendix 7.

Study Period:	Screening	Intervention				EOT	Posttreatment			Notes
Visit Number/Title:	Screening	Cycle 1		Cycle 2 onwards*			Safety FU	Efficacy FU	Survival FU	*Cycles 2 to 17 for Q6W schedule; Cycle 2 to 35 for Q3W schedule.
Cycle Day	Up to 28 days prior to first dose	1	Day 22 (Q6W regimens only)	1	Day 22 (Q6W regimens only)	DC	30 days after last dose			
Scheduling Window (days):	-28 to -1	+3	±3	±3	±3		+7	Q9W ±7	Q12W ±14	
PT/INR and aPTT/PTT (baseline only)	X									Additional testing to be conducted as clinically indicated.
HIV, HBsAg, HCV	X*									*Only if required by local health authority. See country-specific requirements in Appendix 7.
Thyroid Function Tests (TSH, T3, T4), Cortisol, and ACTH**	X		X	X		X	X			Free T3 and Free T4 are acceptable if total T3 and total T4 are unavailable. After C1, retrospective review of thyroid function, ACTH and cortisol testing results is allowed when the results are not available prior to dosing. **ACTH testing is to be done as required per investigator's discretion.
Serum Tumor Marker (CEA)	X	X	X	X		X		X		Dosing permitted prior to results of CEA being known.

Study Period:	Screening	Intervention				EOT	Posttreatment			Notes

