8.11.2 Treatment Period

Visit requirements are outlined in the SoA (Section 1.3). Specific procedure-related details are provided in Section 8.1.

Cohort B participants on Q6W study drug dosing schedule will have a Day 22 visit at each 6-week cycle and undergo assessments as listed in the SoA (Section 1.3).

8.11.3 Participants Discontinued From Study Intervention but Continuing to be Monitored in the Study

Participants who discontinue study treatment due to disease progression or start of a new anticancer therapy will have Safety Follow-up and then proceed directly to Survival Follow-up as described in Section 8.11.4.3.

The End of Treatment Visit should occur at the time study intervention is discontinued for any reason. If the End of Treatment Visit occurs 30 days from the last dose of study intervention, at the time of the mandatory Safety Follow-up Visit, the End of Treatment Visit procedures and any additional Safety Follow-up procedures should be performed. Additional details regarding participant treatment discontinuation can be found in Section 7.1.

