9.6.2 Statistical Methods for Safety Analyses

Safety and tolerability will be assessed by clinical review of all relevant parameters including AEs, laboratory tests and vital signs. Safety analyses will be conducted for each cohort separately.

The analysis of safety results will follow a tiered approach ([Table 12](#)). The tiers differ with respect to the analyses that will be performed. AEs (specific terms as well as system organ class terms) and events that meet predefined limits of change in laboratory and vital signs are either prespecified as “Tier 1” endpoints or will be classified as belonging to “Tier 2” or “Tier 3” based on observed proportions of participants with an event.

Tier 1 Events

CCI

CCI

Tier 2 Events

Tier 2 parameters will be assessed via point estimates with 95% CIs provided for differences in the proportion of participants with events using the M&N method, an unconditional, asymptotic method [Miettinen, O. and Nurminen, M. 1985].

Membership in Tier 2 requires that at least 10% of participants in any treatment group exhibit the event; all other AEs and predefined limits of change will belong to Tier 3. The threshold of at least 10% of participants was chosen for Tier 2 events because the population enrolled in this study is in critical condition and usually experiences various AEs of similar types regardless of treatment; events reported less frequently than 10% of participants would obscure the assessment of the overall safety profile and add little to the interpretation of potentially meaningful treatment differences. In addition, Grade 3 to 5 AEs ($\geq 5\%$ of participants in 1 of the treatment groups) and SAEs ($\geq 5\%$ of participants in 1 of the treatment groups) will be considered Tier 2 endpoints. Because many 95% CIs may be provided without adjustment for multiplicity, the CIs should be regarded as a helpful descriptive measure to be used in safety review, not as a formal method for assessing the statistical significance of the between-group differences.

Tier 3 Events

Safety endpoints that are not Tier 1 or 2 events are considered Tier 3 events. The broad AE categories consisting of the proportion of participants with any AE, a drug-related AE, a serious AE, an AE which is both drug-related and serious, a Grade 3-5 AE, a drug-related Grade 3-5 AE, and discontinuation due to an AE will be considered Tier 3 endpoints. Only point estimates by treatment group are provided for Tier 3 safety parameters.

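### In Cohort B the thyroid/cortisol panel is scheduled twice as often after week 6 in the closed Q3W arms as in the pembrolizumab control, so short-lived endocrine abnormalities may be over-counted against those arms

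*Combined protocol and SAP*

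**What the plan says.** In Cohort B, dosing is "Required every 6 weeks for participants randomized to the MK-1308A or pembrolizumab monotherapy arms" (Section 1.3.2, Table 2, note to Study Medication Administration). The same note sets a 3-week interval for the other three combination arms, MK-4280A, MK-7684A and MK-4830+pembrolizumab. The cycle columns cover "Cycles 2 to 17 for Q6W schedule; Cycle 2 to 35 for Q3W schedule". The Day 22 columns apply to the Q6W regimens alone. Section 8.11.2 confirms that "Cohort B participants on Q6W study drug dosing schedule will have a Day 22 visit at each 6-week cycle", with the assessments marked in the schedule.

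Hematology/chemistry, vital signs and ECOG status are marked at Day 22 of every Q6W cycle. The row "Thyroid Function Tests (TSH, T3, T4), Cortisol, and ACTH" is marked at screening, Cycle 1 Day 22, Day 1 of Cycle 2 onwards, end of treatment and the Safety Follow-up Visit. It is blank at Day 22 from Cycle 2 on. A note leaves ACTH to the investigator, so the fixed part of the panel is thyroid function and cortisol.

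Safety relative to pembrolizumab is a secondary objective for Cohort B (Section 3). Section 9.6.2 sorts AEs, and laboratory values that cross preset limits, into tiers. Tier 2 items get a difference in the proportion of participants affected, with a Miettinen and Nurminen 95% CI. "Membership in Tier 2 requires that at least 10% of participants in any treatment group exhibit the event".

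**The concern.** The proportion of participants with at least one abnormal value depends on how often one looks. For most laboratory and clinical assessments the Day 22 visit gives the Q6W arms the same 3-week rhythm as the Q3W arms. The endocrine panel loses that match after week 6, although the Q6W participants are still seen at Day 22.

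Endocrine toxicity matters for these agents. Section 2.1 lists hypothyroidism among the most common drug-related AEs in the MK-4830 study, and Table 6 gives thyroid and pituitary events their own rows. Section 8.3.5 has clinically relevant laboratory changes recorded as AEs, so denser sampling can reach AE terms as well as laboratory tables. If two regimens had the same true endocrine toxicity, the more densely sampled one could still show the higher proportion. Participants who move to pembrolizumab monotherapy keep their original visit calendar (Section 4.1), so the imbalance continues after a switch.

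**Working it through.** The plan gives no number of endocrine draws and no detection rate, so there is no stated figure to reproduce. The counts below come from Table 2.

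**Step 1. Scheduled on-treatment draws**

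- Q3W: Day 1 of Cycles 2 to 35, at weeks 3, 6, 9, …, 102. That is 34 draws.
- Q6W: Cycle 1 Day 22 (week 3) plus Day 1 of Cycles 2 to 17 (weeks 6, 12, …, 96). That is 1 + 16 = 17 draws.
- After week 6: 34 − 2 = 32 against 17 − 2 = 15.
- Cumulative draws (Q3W / Q6W): week 6, 2 / 2; week 24, 8 / 5; week 52, 17 / 9; week 96, 32 / 17.
- For contrast, hematology/chemistry after Cycle 1 Day 1: 34 (Q3W) against 17 Day 22 draws + 16 Day 1 draws = 33 (Q6W). That row is matched.

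**Step 2. Chance that a scheduled draw catches an abnormality lasting D weeks**

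Assume onset after week 6, uniform within the sampling interval. The probability is min(1, D/3) in Q3W and min(1, D/6) in Q6W.

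| D (weeks) | Q3W | Q6W |
|---|---|---|
| 1 | 33% | 17% |
| 2 | 67% | 33% |
| 3 | 100% | 50% |
| 4 | 100% | 67% |
| 5 | 100% | 83% |
| 6 or more | 100% | 100% |

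A simulation that added the end-of-treatment and Safety Follow-up draws, with treatment stopping at week 24, 52 or 96, gave nearly the same: D = 3, 100% against 50–52%; D = 4, 100% against 67–70%; D = 6 or more, 100% in both.

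**Step 3. Effect on the proportion with an event**

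For D between 3 and 6 weeks, spurious difference = true incidence × share transient × (1 − D/6). Incidence, share and duration are assumptions.

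- All abnormalities last 6 weeks or more: 0 points.
- 10% incidence, 25% transient, D = 4: 10% × 0.25 × 1/3 = 0.8 points.
- 20% incidence, 50% transient, D = 3: 20% × 0.50 × 1/2 = 5.0 points.
- 20% incidence, all transient, D = 3: 20% × 1/2 = 10 points (20% against 10%).

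**Step 4. Isolated chance abnormalities**

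With an assumed independent probability p per draw, P(at least one in k draws) = 1 − (1 − p)^k. By week 52, k = 17 against 9:

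- p = 0.2%: 3.3% against 1.8%
- p = 1%: 15.7% against 8.6%
- p = 2%: 29.1% against 16.6%

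At p = 1% the Q3W figure lies above the 10% Tier 2 threshold and the Q6W figure below it.

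**The case against.** A reader might infer that endocrine rates in the Q3W arms must be higher by construction. The documents do not support that. Only the number of scheduled chances for detection is fixed by the design. An abnormality that persists for 6 weeks or more is found under either schedule; in the Q6W arms it is merely dated up to 3 weeks later. Investigators may order extra tests at any time (Section 10.2), symptoms can prompt testing at the Day 22 visit, and a laboratory finding becomes an AE only if judged clinically significant (Section 10.3.2). These points stand, and they narrow the claim to transient or laboratory-only findings.

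The reach is also limited. All three Q3W arms are closed (Section 4.1), MK-7684A participants were taken off that therapy, and others could switch, so 34 panels is a ceiling. The one Cohort B comparison still open, MK-1308A against pembrolizumab, has Q6W sampling on both sides. The stated objective compares arms with pembrolizumab, so MK-1308A against the other combinations is not a planned safety contrast. Closure does not remove the point, because the Section 3 objectives and the APaT population still include the closed arms.

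Section 9.6.2 treats its intervals as descriptive, and no visible decision rule turns on the 10% threshold. That limits the consequence, but uneven ascertainment shifts the point estimate itself. Finally, Tier 1, Table 12 and part of the opening of Section 9 are redacted. It cannot be said that the plan handles endocrine limits without adjustment, only that the visible text shows none.

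**Conclusion.** The concern holds in a limited form. After week 6 the scheduled thyroid/cortisol panel is drawn twice as often in the MK-4280A, MK-7684A and MK-4830+pembrolizumab arms as in the pembrolizumab control. Endocrine abnormalities lasting less than 6 weeks may therefore be over-counted in those arms in the Section 9.6.2 proportions. The draw counts follow directly from Table 2. The size does not: it runs from zero, if abnormalities persist, to about two-fold for short-lived findings. The point figures in Steps 3 and 4 rest on assumed incidence, duration and per-draw probability. The bias, where present, runs against the closed arms and leaves MK-1308A against pembrolizumab untouched.

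**What to change.** Keep the all-sample safety analysis. In Section 9.6.2 or the sSAP, add a second comparison of each Q3W arm with pembrolizumab for TSH, T3, T4 and cortisol limits of change. Restrict it to the draws scheduled in both regimens: weeks 3, 6, 12, 18, …, 96, end of treatment and Safety Follow-up. That leaves 17 on-treatment draws on each side over a full course. Panels follow cycle Day 1, so assign draws to these weeks with visit windows that allow for dose delays. State that endocrine differences will be read in light of both versions.

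Showing AE differences at Grade 2 or higher beside any grade would not equalize sampling and is no substitute.

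The cost is a short paragraph, a windowed visit filter and one further table. The restricted version loses some sensitivity for short events in the Q3W arms, which is why it should sit beside the all-sample result and not replace it. No new procedure is needed.

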1.3.3 Second Course Treatment

Table 3 Study Schedule of Activities – Second Course Treatment

[figure not shown]
Study Period:	Intervention		EOT	Posttreatment			Notes
Visit Number/Title:	Cycle 1	Cycles 2 to 17 (2 to 9 for Q6W schedule)		Safety FU	Efficacy FU	Survival FU	
Cycle Day	1	1	DC	30 days after last dose			
Scheduling Window (days):	±3	±3		+7	Q9W ±7	Q12W ±14	
Administrative Procedures							
Eligibility Criteria	X						
Concomitant Medication Review	X	X	X	X			Record concomitant medications beyond 30 days after treatment discontinuation if related to an SAE or ECI.
Study Intervention Administration	X	X*					*Required every 6 weeks for participants randomized to the MK-1308A or pembrolizumab monotherapy arms and every 3 weeks for participants randomized to the MK-4280A, MK-7684A, or MK-4830+pembrolizumab arms. Refer to Section 6.1.1.2 for Second Course treatment information for participants in closed arms.
Progression and Subsequent Antineoplastic Therapy Status			X	X	X	X	All progression events and anticancer therapy will be recorded during follow-up until time of death or termination of survival follow-up. If a clinical visit is not feasible, follow-up information may be obtained by other means such as telephone or email. Not required for participants in closed arms.

MK-1308A-008-05 FINAL PROTOCOL
08VH4V

Study Period:	Intervention			EOT	Posttreatment			Notes
Visit Number/Title:	Cycle 1	Cycles 2 to 17 (2 to 9 for Q6W schedule)			Safety FU	Efficacy FU	Survival FU	
Cycle Day	1	1		DC	30 days after last dose			
Scheduling Window (days):	±3	±3			+7	Q9W ±7	Q12W ±14	
12-lead ECG	X	X*	X					*As clinically indicated.
ECOG Performance Status	X	X	X		X			Must be performed before treatment at each cycle.
AE/SAE review								AEs monitored up to 30 days after last dose. SAEs monitored up to 90 days and pregnancy monitored up to 120 days after last dose, or 30 days after last dose if participant starts a new anticancer therapy, whichever is sooner. Participants on the 6 weeks dosing schedule will require a safety phone call at C1D22. The site is to record the call and any findings in the source documents. Further procedures / tests are to be scheduled by the site as clinically indicated and entered in an “unscheduled visit” module in the CRF. Refer to Section 8.3 for safety monitoring information for participants in closed arms.
Laboratory Assessments								
Hematology/Chemistry	X*	X	X	X				Collect predose. *Collect within 72 hours before C1D1 study intervention dose.
Urinalysis	X	X*	X*	X				*As clinically indicated.
Serum or Urine Pregnancy test (WOCBP only)	X	X	X	X				WOCBP require a negative test prior to C1. If more than 24 hours for a urine test or 72 hours for a serum test have elapsed prior to the first dose of study intervention, another pregnancy test is required. See country-specific requirements in Appendix 7.

Study Period:	Intervention		EOT	Posttreatment			Notes
Visit Number/Title:	Cycle 1	Cycles 2 to 17 (2 to 9 for Q6W schedule)		Safety FU	Efficacy FU	Survival FU	
Cycle Day	1	1	DC	30 days after last dose			
Scheduling Window (days):	±3	±3		+7	Q9W ±7	Q12W ±14	
PT/INR and aPTT/PTT (baseline only)	X						Within 72 hours of the first dose. Additional testing to be conducted as clinically indicated.
Thyroid Function Tests (TSH, T3, T4), Cortisol, and ACTH**		X	X	X			Free T3 and Free T4 are acceptable if total T3 and total T4 are unavailable. Retrospective review of thyroid function, ACTH and cortisol testing results is allowed when the results are not available before dosing. **ACTH testing is to be done per investigator's discretion.
Serum Tumor Marker (CEA)	X	X	X		X		Dosing permitted prior to results of CEA being known.

Biomarkers

ACTH= adrenocorticotrophic hormone; AE=adverse event; aPTT=activated partial thromboplastin time; BP=blood pressure; C=cycle; CEA=carcinoembryonic antigen; CT=computed tomography; ctDNA=circulating tumor deoxyribonucleic acid; D=day; DBP=diastolic blood pressure; DC=discontinuation; ECG=electrocardiogram; ECI=event of clinical interest; ECOG=Eastern Cooperative Oncology Group; EOT=end of treatment; FU=follow-up; HR=heart rate; INR=international normalized ratio; MRI=magnetic resonance imaging; PT=prothrombin time; PTT=partial thromboplastin time; Q6W=every 6 weeks; Q9W=every 9 weeks; Q12W=every 12 weeks; RNA=ribonucleic acid; RR=respiratory rate; SAE=serious adverse event; SBP=systolic blood pressure; SpO2=oxygen saturation; T3=triiodothyronine; T4=thyroxine; TSH=thyroid-stimulating hormone; WOCBP=women of childbearing potential.

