Cycle Day	Up to 28 days prior to first dose	1	22	1	22	1	DC	30 days after last dose			
Scheduling Window (days):	-28 to -1	+3	±3	±3	±3	±3		+7	Q9W ±7	Q12W ±14	
Thyroid Function Tests (TSH, T3, T4), Cortisol, and ACTH**	X	X*	X	X		X	X	X			Free T3 and Free T4 are acceptable if total T3 and total T4 are unavailable. After Cycle 1, retrospective review of thyroid function, ACTH and cortisol testing results is allowed when the results are not available before dosing. *Collection is optional on C1D1. **ACTH testing is to be done as required per investigator's discretion
Serum Tumor Marker (CEA)	X	X		X		X	X		X		Dosing permitted prior to results of CEA being known.

PK/ADA/Biomarkers

CCI

Study Period:	Screening	Intervention (Q6W)					EOT	Posttreatment			Notes
Visit Number/Title:	Screening	Cycle 1		Cycle 2		Cycles 3 to 17		Safety FU	Efficacy FU	Survival FU	
Cycle Day	Up to 28 days prior to first dose	1	22	1	22	1	DC	30 days after last dose			
Scheduling Window (days):	-28 to -1	+3	±3	±3	±3	±3		+7	Q9W ±7	Q12W ±14	

CCI

ACTH=adrenocorticotrophic hormone; ADA=antidrug antibodies; AE=adverse event; aPTT=activated partial thromboplastin time; BP=blood pressure; BRAF=B-Raf gene; C=cycle; CEA=carcinoembryonic antigen; CT=computed tomography; (ct)DNA=(circulating tumor) deoxyribonucleic acid; D=day; DBP=diastolic blood pressure; DC=discontinuation; ECG=electrocardiogram; ECI=event of clinical interest; ECOG=Eastern Cooperative Oncology Group; EORTC QLQ-C30=European Organisation for Research and Treatment of Cancer Quality of Life Questionnaire; EOT=end of treatment; (e)PRO=electronic patient-reported outcome; EQ-5D-5L=EuroQoL 5-dimension, 5-level scale; FU=follow-up; HBsAg=Hepatitis B surface antigen; HCV=Hepatitis C virus; HIV=human immunodeficiency virus; HR=heart rate; INR=international normalized ratio; IRT=interactive response technology; KRAS=Kirsten rat sarcoma viral oncogene homolog; MMR=mismatch repair; MRI=magnetic resonance imaging; MSI=microsatellite instability; NAb=neutralizing antibody; PRO=patient-reported outcome; PT=prothrombin time; PTT=partial thromboplastin time; Q6W=every 6 weeks; Q9W=every 9 weeks; Q12W=every 12 weeks; RAS=genes that makes the proteins called KRAS, HRAS, and NRAS; RNA=ribonucleic acid; RR=respiratory rate; SAE=serious adverse event; SBP=systolic blood pressure; SoA=schedule of activities; SpO2=oxygen saturation; T3=triiodothyronine; T4=thyroxine; TSH=thyroid-stimulating hormone; WOCBP=women of childbearing potential.

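### Second Course has no thyroid/cortisol panel at or before Cycle 1, so re-treatment starts without a current endocrine value

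*Combined protocol and SAP*

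**What the plan says.** Table 3 (Section 1.3.3) lists the row "Thyroid Function Tests (TSH, T3, T4), Cortisol, and ACTH". It is blank at Cycle 1, marked at Cycle 2 onward, End of Treatment and Safety Follow-up, and blank at Efficacy and Survival Follow-up. Its note adds: "Retrospective review of thyroid function, ACTH and cortisol testing results is allowed when the results are not available before dosing". ACTH is left to the investigator.

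In the same table, hematology/chemistry is marked at Cycle 1 with the instruction "Collect within 72 hours before C1D1 study intervention dose". At Day 22 of the first cycle the plan asks for a contact and no blood draw: "Participants on the 6 weeks dosing schedule will require a safety phone call at C1D22".

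For First Course, Table 1 (Cohort A) and Table 2 (Cohort B) both mark the panel at Screening. Their notes restrict late review of results to later cycles: "After Cycle 1, retrospective review of thyroid function, ACTH and cortisol testing results is allowed when the results are not available before dosing" in Cohort A, and in nearly the same words in Cohort B, "After C1, retrospective review of thyroid function, ACTH and cortisol testing results is allowed when the results are not available prior to dosing".

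**The concern.** Second Course participants come back to checkpoint inhibition after a treatment-free interval that ends at progression and has no stated upper limit. Section 6.6.1 itself warns that immune-related events can appear several months after treatment stops. Collection of nonserious adverse events ends 30 days after the last dose (Section 8.4.1), and Efficacy Follow-up includes no endocrine test.

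A participant who developed thyroid, adrenal or pituitary dysfunction without symptoms in that interval would be re-dosed without anyone having been asked to look. When the first Second Course panel comes back abnormal, the only values to compare it with date from First Course. What is at stake is earlier detection of a few conditions that would change management, and a better date of onset for events first seen in Second Course.

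**Working it through.** No sample size, power or error rate is involved. The check is a cell-by-cell reading of the three schedules, a search for any other rule that would require the test, and date arithmetic.

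**1. The endocrine row in each schedule**

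| Schedule | Before first dose | First panel after first dose |
|---|---|---|
| Table 1, Cohort A (Q6W) | Screening required; Cycle 1 Day 1 optional | Cycle 1 Day 22 |
| Table 2, Cohort B | Screening required; Cycle 1 Day 1 blank | Cycle 1 Day 22 on Q6W; Cycle 2 Day 1 on Q3W |
| Table 3, Second Course | None | Cycle 2 Day 1 |

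Scheduled and required panels before the first dose: 1 in First Course, 0 in Second Course. ACTH is discretionary throughout, so the required part of the gap is the thyroid tests and cortisol.

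**2. Is the blank cell a text-extraction fault?** The row carries all six visit cells. The neighbouring coagulation row, labelled as a baseline test, has its single mark under Cycle 1, and the CEA row also lines up with the header. The blank is genuine.

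**3. The other visible laboratory rows of Table 3 at Cycle 1.** Hematology/chemistry, urinalysis, pregnancy test, coagulation and CEA are marked; the endocrine panel is not. That is 5 of 6, so Cycle 1 serves as the baseline column for everything else. In Table 2, the ECG, coagulation and endocrine rows are all marked at Screening and blank at Cycle 1 Day 1. In Table 3 the ECG and coagulation marks appear at Cycle 1 and the endocrine mark does not. I infer an oversight in moving the screening items across; the documents give no reason either way.

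**4. Does other text require the test?**
- Section 6.1.1.2 re-applies the eligibility criteria, but no criterion in Sections 5.1 or 5.2 calls for a thyroid or cortisol result.
- Table 4 covers hematological, renal, hepatic and coagulation function only.
- Section 8.3.5 refers to the schedule of activities for timing.
- Appendix 2 allows dosing while thyroid results are pending but schedules no Second Course baseline. Appendix 7 adds none.
- Section 8.11.4.2 moves participants straight from Efficacy Follow-up into Second Course.

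**5. Timing**
- Last scheduled panel before restart: First Course Safety Follow-up, 30 days (+7) after the last dose.
- First panel after restart, Q6W (both open arms): 42 ±3 days, so 39 to 45 days. In First Course on Q6W it is Day 22, which is 21 days after Day 1, so Second Course is 42 − 21 = 21 days later.
- First panel after restart, Q3W (closed arms): 21 ±3 days, so 18 to 24 days.
- Interval between consecutive scheduled panels on Q6W = t + 42 days, where t is the time from Safety Follow-up to restart. The plan sets no upper limit on t. As an illustration only, if t equals one scan interval (63 days), the interval is 63 + 42 = 105 days.

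**The case against.** The strongest reply is that the gap does little harm, and much of that reply stands.

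- **There is other cover.** Eligibility is re-checked, including recovery from earlier toxicities. ECOG status and chemistry (with sodium, potassium and glucose) are obtained at Cycle 1, and Section 8.3.1.2 provides a directed examination as clinically indicated. Cohort A has a directed examination at Efficacy Follow-up, possibly remote. Table 3 also says "Further procedures / tests are to be scheduled by the site as clinically indicated". These measures serve participants with symptoms or electrolyte disturbance. They do not look for silent disease.
- **Many silent thyroid findings would not alter dosing.** Table 6 continues treatment for Grade 2 hyperthyroidism and Grade 2 to 4 hypothyroidism, and eligibility tolerates endocrine events up to Grade 2 on replacement. That is right. What remains is hypophysitis, withheld from Grade 2, and Grade 3 or 4 hyperthyroidism, withheld or discontinued.
- **First Course leaves a long series of values.** It does, so an abnormal Cycle 2 result is not without reference. The reference may simply be old.

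Three stronger readings are tempting and are not supported.

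- A reader might infer that events arising off treatment would be wrongly recorded as Second Course adverse events. Section 10.3.2 counts a condition first detected after dosing as an adverse event even if it was there before, so such recording follows the plan's own rule.
- A reader might infer the same gap for lipase and amylase. Appendix 2 places them within the chemistry panel, which is marked at Second Course Cycle 1. The footnote naming screening, End of Treatment and 30-day follow-up is at most ambiguous for Second Course.
- A reader might want the result to gate the first Second Course dose. Tables 1 and 2 limit late review to later cycles, but Table 3 carries no such limit and Appendix 2 permits dosing with thyroid results pending. The case made here is for a baseline and earlier detection, and it does not need a gate.

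**Conclusion.** The point holds as a small but real gap in safety monitoring. Followed exactly, the plan re-doses participants with no endocrine panel scheduled since First Course Safety Follow-up, and takes the first new one 42 ±3 days later on Q6W or 21 ±3 days later on Q3W. The consequence is later detection of silent thyroid or adrenal/pituitary dysfunction and weaker dating of its onset. Second Course responses and progressions do not count toward the primary analysis (Section 6.1.1.2), and a misjudged onset date does not move an event between arms, so ORR and the between-arm comparisons are unaffected.

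The number affected is not stated. A reader might carry over the 9 re-exposed patients among 61 + 63 = 124 in KEYNOTE-164 (9/124 = 7.3%, Sections 2.1 and 4.2.5). That is a count from another trial in previously treated patients, whose follow-up and re-treatment rules are not described here. It supports no more than the expectation that few will be re-treated. The documents give no rate of silent endocrine events, so no event count is claimed. The recommendation rests on the low cost of the change and not on either number.

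**What to change.** In Table 3, mark the thyroid/cortisol row at Second Course Cycle 1, collected predose with the hematology/chemistry sample already taken in the 72 hours before that dose. Leave ACTH at the investigator's discretion and keep retrospective review of results, so that the first dose is not delayed.

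The cost is one edit to the schedule and a few added analytes for re-treated participants. It needs no new visit or procedure and no change to any analysis.
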